18 the data files. Study computers are password protected and encrypted. With regard to
19 electronic information, the server will be protected from outside intrusion by multiple firewalls.
20 Administrative access to the machines will only occur using SSH, a secure, encrypted protocol
21 for remotely connecting to a machine. The servers will be hardened against attack using some of
22 the concepts deployed in the Bastille Linux project, a project whose purpose is to automate some
23 of the processes involved in hardening the Linux operating system. Security will be periodically
24 monitored using network mapping tools, like nmap which probe machines for vulnerabilities and
25 report the results to the system administrator. The software Port Scan Attack Detector (PSAD)
26 will be used to monitor the servers and notify administrators if they come under attack. The
27 Advanced Intrusion Detection Environment (AIDE) will be used to detect if any unauthorized
28 changes are made to the machine, allowing us to identify and fix changes that might be made to
29 critical files in the unlikely event of a break-in. Servers will be backed up nightly to external
30 hard drives using an encrypted file system. External hard drives will be rotated offsite weekly
31 and stored in the PD's office in a locked, data-safe firebox. The software vendors/developers
32 websites will be monitored for security patches and upgrades. Additionally, the server
33 appliance's Linux operating system provides a means for monitoring and regularly installing
34 security patches. See the Data Monitoring Plan for further information about protection against
35 risks. As staff training is crucial to ensuring confidentiality, all study personnel will receive
36 certification in human subjects' protection from the Collaborative Institutional Training Initiative
37 (CITI) prior to beginning work on this project.

38

39 **Auditing procedures**

40 Review of any problems related to quality of data collection, transmission or analyses, and of
41 any AEs and SAEs that occurred during the past week will occur at weekly research staff
42 meetings held by Drs. [name], [name], and [name] at UVM.

43

44 **Adverse Event (AE) and Unanticipated Problem (UAP) Reporting**

45 In the proposed study, we will use the FDA's definition of AEs and SAEs. AEs and SAEs will be
46 assessed at each subject visit by a trained staff member, and will be discussed at the weekly

1 research staff meetings. Any SAE will be brought to the attention of the PI as soon as possible
2 and not longer than 24 hours. Any AE or SAE that is both unexpected and related to the study
3 participation will be reported to the IRB within 7 days of the event. That IRB will make a
4 determination as to whether additional reporting requirements are needed. IRB actions will be
5 reported to the funding agency by the PI no less than annually and more frequently as
6 recommended by the local IRB. Any SAEs will be summarized in the yearly Progress Reports to
7 the funding agency, including a review of frequency and severity. All SAEs will be followed
8 through ongoing consultation with the physician caring for the patient until they resolve, result in
9 death, or stabilize and are not expected to improve.

10

11 **Withdrawal Procedures**

12 Women will be free to withdraw at any point during the course of the study without penalty.
13 That will be explained during informed consent. In terms of data analysis, we will adhere to an
14 intent-to-treat approach (Armitage, 1983) wherein all women randomized to the study conditions
15 will be included in the analyses independent of early dropout, noncompliance, etc., with the
16 exception of excluding women for abortion/fetal demise prior to their late pregnancy smoking
17 assessment. Women who receive their equipment and fail to complete an orientation session, as
18 well as women who provide a baseline CO sample indicating that they are non-smokers, will be
19 withdrawn prior to randomization and thus not included in an intent-to-treat analysis.

20

21 **Sources of Materials**

22 The research materials to be obtained include interviews, questionnaires, and breath and saliva
23 specimens to verify smoking status (and serve as the basis for reinforcement in the incentives
24 condition). Materials will be collected remotely using a combination of phone calls with
25 participants, online surveys, and remote video capture via smartphone app (i.e., for submission of
26 breath CO samples and salivary cotinine samples). These data will be entered into databases with
27 no identifying information (i.e., with subject ID only). These databases are stored on password-
28 protected external hard drives in locked offices in a locked clinic accessible only to the PI and
29 research staff.

30

31 **SUBJECT CHARACTERISTICS, IDENTIFICATION AND RECRUITMENT**

32

33 **Subject Selection**

34 We are studying Alaska Native pregnant women who are currently cigarette smokers to develop
35 more effective interventions to help this population quit smoking. As noted previously, the
36 frequent biochemical verification required by in-person financial incentives interventions often
37 limits the number of individuals we can treat, as some women live in remote areas and/or lack
38 reliable transportation to a clinic. Targeting pregnant smokers in a remotely delivered
39 intervention may provide an innovative means of transcending these historical barriers to
40 treatment. Additionally, smoking prevalence is substantially higher among Alaska Native
41 pregnant women (i.e., ~ 36% [[name] et al. 2018] versus ~ 13% among U.S. pregnant women
42 overall [[name] et al., 2017]), they exhibit unique tobacco use characteristics including use of a
43 homemade smokeless tobacco (Iqmik, Hurt et al., 2009), and very few smoking cessation
44 interventions have been implemented specifically among Alaska Native women ([name] et al.,
45 2010; [name] et al., 2018). Thus, the proposed pilot study represents the first examination of the
46 feasibility and effectiveness of financial incentives to reduce smoking targeting this specific

1 population and may provide important preliminary data for future grant applications to
2 disseminate the present intervention among Alaska Native women on a larger scale.
3

4 **Vulnerable Populations**

5 Pregnant women to develop more effective interventions to help them quit smoking.
6

7 **Number of Subjects**

8 60 Alaska Native women.
9

10 **Inclusion/Exclusion Criteria**

11 A total of 60 Alaska Native pregnant women will be recruited. The inclusion criteria include: (a)
12 ≥ 18 years of age, (b) report being smokers at the time they learned of the current pregnancy, (c)
13 report smoking in the 7 days prior to completing their initial eligibility screening, (d) ≤ 25 weeks
14 pregnant, (e) speak English, (f) own a smartphone (Android or iOS; 81.8% of pregnant women in
15 wave 1 [2013-2014] of the Population Assessment of Tobacco and Health [PATH] reported
16 owning a smartphone). The exclusion criteria include: (a) current or prior mental or medical
17 condition that may interfere with study participation (assessed via self-report), (b) smoke
18 marijuana more than once each week and not willing to quit (marijuana smoking can inflate
19 breath CO), (c) exposed to unavoidable occupational sources of CO (e.g., car mechanic), and (d)
20 currently maintained on opioid maintenance therapy. The only criteria for withdrawing someone
21 from the trial following randomization to treatment condition will be pregnancy termination or
22 fetal demise prior to participants' late-pregnancy smoking assessment (≥ 28 weeks gestation).
23 Women who fail to complete an orientation session or provide an initial CO sample indicating
24 that they are smokers will be withdrawn prior to randomization. Criteria will be assessed during
25 an initial eligibility screen that can be conducted either online or by phone to determine
26 preliminary eligibility and further evaluated during the formal intake assessment.
27

28 **Inclusion of Minorities and Women**

29 This project will include only women. Smoking among pregnant and newly postpartum women
30 has sufficiently special circumstances regarding the potential toxicity to the fetus and newborn,
31 the reasons for trying to quit smoking and prevent relapse, and the patterns of smoking reduction,
32 cessation, and relapse that they need to be studied exclusively in women.
33

34 Additionally, the project will include only Alaska Native women. However, should we receive
35 referrals from non-Alaska Native women in Alaska who are pregnant and currently smoking, we
36 will refer them to the Alaska tobacco quit line.
37

38 **Recruitment**

39 As in prior and current trials conducted at UVM, including the ongoing parent trial, applicants
40 will be recruited from online media advertisements. The text for these ads, as well as exemplars
41 of pictures, are attached to this submission. These ads were developed based on prior research
42 conducted by the ANTHC involving online recruitment of Alaska Native women. These ads will
43 include a link to the preliminary screening questions administered through REDCap. If eligible,
44 we will collect the participant's contact information and schedule a time to contact them to
45 provide more information about the study and conduct the consent phone call if they choose to
46 enroll.

1
2
3
4

FINANCIAL CONSIDERATIONS

5

Expense to Subject

6 No known expense to subject aside from their time.
7

8

Payment for Participation

9 Women in both conditions will receive compensation for completing 7 formal assessments at
10 \$50/assessment = \$350. Women assigned to the best practices plus incentives condition will
11 have the potential to earn incentives in the form of money loaded onto a PEX Debit Card for
12 abstaining from smoking. The incentives that participants earn will vary depending on how early
13 in the pregnancy she enters the study and how well she abstains from smoking. However, the
14 maximum potential amount that a woman could earn is approximately \$1620 in incentives. This
15 total is equivalent to the maximum total earnings in prior UVM trials adjusted for inflation
16 (\$1,200 in 2002 USD = \$1,600 today).
17

18

Collaborating Sites

19 The present study represents a collaboration between University of Vermont (Project PI-[name]
20 [name], PhD & Center [name]) and the Alaska Native Tribal Health
21 Consortium (ANTHC), Anchorage Alaska. The Site Principal Investigator for the ANTHC is
22 [name], Ph.D. [name] research focuses on developing novel, theory-based
23 behavioral interventions for tobacco cessation, including NIH-supported intervention programs
24 to reduce tobacco disparities among Alaska Native adolescents and pregnant women. The co-
25 investigators at the ANTHC are [name], MD (ANTHC), [name], PhD
26 (Mayo Clinic, Rochester, MN), and [name], MD (ANTHC). UVM IRB approvals,
27 as well as the Human Subjects Research Protocol currently on file at UVM, are attached to this
28 submission.
29

30

31

INFORMED CONSENT

32

Consent Procedures

33 With respect to the informed consent process, eligible participants will be given detailed
34 information about the study including the following: (a) each study condition; (b) cash
35 compensation for their time (e.g., completing assessments); (c) the process of randomization and
36 the equal chance of being assigned to one of the two study conditions; (d) protection of
37 confidentiality and the right to withdraw at any time; (e) expectations regarding the completion
38 of formal assessments during and following their delivery (regardless of smoking status); (f)
39 risks and benefits of study participation; and (g) our procedures for dealing with any
40 endorsement of suicidality or self-harm. Contact information for the Project Postdoctoral
41 Fellow/Primary Project Contact ([name]), the Project Research Associate in Alaska at the
42 ANTHC ([name]), the Project PI ([name]), Site PI ([name]), and the contact
43 person at the Alaska Area IRB will be provided during the verbal consent as well as included in
44 the paper copy of the Informed Consent Form that is mailed to subjects' homes. Participants will
45
46

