33 inflate breath CO), (c) exposed to unavoidable occupational sources of CO (e.g., car mechanic),
34 and (d) self-report currently being maintained on opioid maintenance therapy (e.g., methadone,
35 buprenorphine).

36
37 Participants randomized to the Best Practices plus Incentives condition will select a quit date
38 (either the first or second Monday following their enrollment), and will submit videos of
39 themselves blowing into a breath CO monitor twice daily during week 1. They will receive
40 incentives for every sample where expired breath CO is ≤ 6 ppm. Beginning in week 2 and
41 extending through week 6, participants will submit videos twice per week (Monday/Thursday)
42 for which they will receive incentives for providing videos of themselves completing saliva
43 cotinine tests indicating smoking abstinence. From week 7 until delivery, participants will
44 submit videos once per week and will continue to receive incentives for saliva cotinine tests
45 indicating no smoking. During the postpartum period, women will submit videos twice weekly
46 for the first 4 weeks and once weekly from weeks 5-12. The first negative breath CO or salivary

1 cotinine sample is worth \$6.25 and each consecutive negative sample will increase the value of
2 the incentive by \$1.00 up to a maximum of \$33.25 per sample. Missed samples or samples that
3 indicate smoking will be worth \$0 and will reset the incentive at its starting value (i.e., \$6.25).
4 However two consecutive negative samples following the slip will restore the incentive to its
5 value before the slip. The maximum earnings in this condition is \$1,620, which is the same as
6 our prior studies adjusting for inflation. A proposed incentive schedule is attached.
7

8 Women in both conditions will complete seven formal assessments of their smoking status
9 during their participation (intake, early pregnancy or 1 month after enrollment, late pregnancy or
10 ≥ 28 weeks gestation, and at 4-, 8-, 12-, and 24-weeks postpartum) along with a treatment
11 acceptability questionnaire and semi-structured interview on barriers and facilitators of treatment
12 engagement. Women will receive \$50 for completing each of these (\$350 total).
13

14 As the proposed study is the first examination of smartphone-based financial incentives for
15 reducing smoking during pregnancy among Alaska Native women, it represents an exploratory

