23 7 days prior to completing their preliminary eligibility screening, (d) \leq 25 weeks pregnant, (e)
24 speak English, (f) own a smartphone (Android or iOS; 81.8% of pregnant women in wave 1
25 [2013-2014] of the Population Assessment of Tobacco and Health [PATH] reported owning a
26 smartphone). Exclusion criteria include: (a) current or prior mental or medical condition that
27 may interfere with study participation (assessed via self-report during formal intake assessment
28 completed online or by phone using a medical and psychosocial history questionnaire), (b)
29 smoke marijuana more than once each week and not willing to quit (marijuana smoking can
30 inflate breath CO), (c) exposed to unavoidable occupational sources of CO (e.g., car mechanic),
31 (d) report currently receiving opioid maintenance therapy (e.g., methadone, buprenorphine).
32 Women who meet the inclusion criteria and complete the informed consent process will be
33 considered formally enrolled and will be mailed equipment to participate in the study, but will
34 not be randomized until they (1) confirm receipt of their equipment, (2) complete an orientation
35 session on the smartphone app used in the current study (described subsequently), and (3)
36 provide a saliva sample indicating current smoking (i.e., test strip returns a positive for cotinine,
37 a metabolite of nicotine). Upon completing these steps, women will be randomized to either the
38 best practices plus incentives condition or best practices control condition (See Treatment
39 Conditions). The only criteria for withdrawing participants after randomization occurs will be
40 pregnancy termination or fetal demise.

41
42 **General Study Procedures.**

43 **Orientation Session:** After verifying eligibility and completing the informed consent process,
44 participants will be mailed two saliva test kits. Upon receiving the saliva tests, research staff will
45 aid participants in setting up their profile (e.g., create an account, upload profile photo) on the
46 DynamiCare smartphone application (“app”) which is used to submit breath and saliva samples

1 remotely. Participants will be trained in the operation of the app and will have the opportunity to
2 practice submitting saliva samples. The first sample that participants submit upon receiving their
3 saliva test kits will be used to validate smoking status and participants will be withdrawn prior to

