29 completing the quiz. Participants will select a quit date during orientation (either the first
30 Monday following the call or the next Monday), and research staff will contact them by phone
31 on the Friday prior to their quit date. Staff will also inform participants to contact them in the
32 event that their phone is lost, stolen, or broken. In sum, participants who complete the informed
33 consent process will be mailed two saliva test kits to verify their smoking status prior to being
34 assigned to one of the two treatment conditions. Two tests will be sent in case participants' first
35 sample is invalid (e.g., insufficient saliva to produce a reading) and they need to complete a
36 second test to verify smoking status. Participants who are verified to be smokers will then
37 complete the treatment assignment phone call, after which study staff will provide them with the
38 equipment that they will need for the remainder of the study (e.g., breath CO monitor and
39 additional saliva test kits).

40
41 **Mobile-Phone Based Financial Incentives:** The intervention will be delivered on participants'
42 smartphones via an app installed on their phone either before or during the orientation session.
43 The process of submitting a video entails the following steps: (1) Participant opens the app,
44 which requires them to type in a password. Their username and password (stored as a secure,
45 “irreversible” one-way hash) will be stored in a configuration file accessible only to the
46 application; (2) The app will verify the password and participants will be taken to the “home”

1 screen which will show their cumulative earnings to date and a “post video” button; (3) The app
2 will attempt to contact the server over the Internet (via a 3G/4G mobile network) to determine
3 the correct time and status of the participant; (4) The participant will click on the post video
4 button, thereby leading them to a simple interface for recording videos that contains a start/stop
5 recording toggle button, a play button to review the recorded video, and a post button to send the
6 video to the server; (5) After posting the video, the server will display a voucher based on the
7 voucher schedule cached from the prior video upload. The app will then create a text file
8 containing a timestamp and video file. These files will be archived, compressed, and encrypted
9 to prevent tampering and/or eavesdropping while in transit. The app will maintain a file lock on

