38 participant. In contrast, the technology-based method that we are proposing is easy to implement
39 and will decrease both staff travel time to redeem incentives, as well as the immediacy between
40 engaging in the target behavior and receiving reinforcement.

41

42 **Assessment Procedures.** Participants in both the best practices plus incentives condition and the
43 best practices control condition will complete a formal assessment at intake, during early
44 pregnancy (i.e., one month after enrolling), late pregnancy (i.e., 28-weeks gestation), and at 4-,
45 8-, 12-, and 24-weeks postpartum. This schedule of formal assessments and the use of similar
46 questionnaires (see Assessment Battery) will permit comparisons to prior controlled trials

1 conducted by UVM researchers.^{15,45-48} Participants will receive \$50 per formal assessment
2 completed regardless of their smoking status. This money may come in the form of a check
3 mailed to their home or in the form of a gift card (TangoCard) that is emailed to them.
4 TangoCard is an electronic gift card platform. If participants receive their rewards via this
5 option, the reward will be emailed to them as a unique URL. By following the URL, the
6 participant can choose from a variety of gift card brands and redeem their reward. Once they
7 select a brand, the final gift card will be emailed to them. To ensure that HIPAA security
8 standards are met and emails are kept private, TangoCard has signed a BAA (Business Associate
9 Agreement) with DynamiCare. Questionnaires will be completed remotely via computer or
10 mobile phone. Items will be administered using REDCap or SurveyGizmo, both of which
11 capture and house unique de-identified codes for study participants. Data audits will be
12 conducted monthly during the first six months of the study and then quarterly until study
13 completion to detect problems. As no personal identifying information will be collected, the
14 chance of a breach of confidentiality is very low. Regardless of whether participants complete
15 the assessment online or over the phone, participants in both treatment conditions will be
16 required to submit both a breath CO sample and a salivary cotinine sample at each formal
17 assessment to determine their smoking status.
18

19 **Assessment Battery** Participant's intake assessment will be conducted after they have completed
20 a preliminary eligibility screening and appear to be eligible, and will address seven areas: (a)

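### The early and late pregnancy assessments are timed from consent and from gestational age, with no minimum interval after treatment starts, so their order can reverse and some can fall in or before the quit week

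*Combined protocol and SAP*

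**What the plan says.** All references are to the combined protocol and SAP.

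- **Visit timing.** Assessment Procedures places the early and late visits at "pregnancy (i.e., one month after enrolling), late pregnancy (i.e., 28-weeks gestation), and at 4". The opening summary instead gives the late visit as "≥ 28 weeks gestation, and at 4-, 8-, 12-, and 24-weeks postpartum) along with a treatment", and Inclusion/Exclusion Criteria agrees with the summary: "fetal demise prior to participants' late-pregnancy smoking assessment (≥ 28 weeks gestation".
- **Enrolment.** Under Procedures, Participants, a woman who meets the criteria and consents is "considered formally enrolled and will be mailed equipment to participate in the study, but will" "not be randomized until they (1) confirm receipt of their equipment, (2) complete an orientation" session and give a cotinine-positive saliva sample. Entry is open up to 25 weeks.
- **Quit date.** Orientation Session states: "Participants will select a quit date during orientation (either the first" Monday after the call or the one after that). Treatment Conditions says the same. The opening summary counts from a different event: "either the first or second Monday following their enrollment), and will submit videos of".
- **Sampling.** Both arms give breath CO and saliva cotinine at every formal assessment. Treatment Conditions accepts that cotinine falls more slowly than CO over week 1.
- **Use of the visits.** Statistical Methods compares abstinence at the end of pregnancy by Cochran-Mantel-Haenszel test and across all assessments by GEE. It divides the cost difference by the late-pregnancy difference in abstinence. Both sample-size statements (opening summary and Sample Size Justification) refer to late-pregnancy abstinence.

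No section sets a minimum time between the quit date, or the call, and either visit.

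**The concern.** Treatment starts at the quit date, which depends on the orientation call. Neither visit does: one clock starts at consent and the other at conception. A woman who enters late, or whose kits arrive slowly, can reach a visit before she has had a fair chance to quit. A woman seen before her quit date cannot yet have earned an incentive. One seen in the quit week may have stopped smoking and still test cotinine-positive.

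Such visits dilute the difference between the arms. Late-pregnancy abstinence is one of several primary measures. It is also the effect side of the cost-effectiveness ratio, and the results are meant to inform power calculations for a larger trial, so any dilution carries forward. The early visit enters the GEE, where a reversed order of early and late visits would also blur what the two labels mean.

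**Working it through.** **Inputs from the documents.** Entry up to 25 weeks, run as 25w0d (day 175 of gestation) and 25w6d (day 181). The late visit at 28w0d is day 196. The quit date falls q = 1 to 14 days after the call. The quit week is 7 days. There are 60 women, 30 per arm.

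**Assumptions, because the documents give no figure.** The lag L from consent to the call is 7, 14 or 21 days. Entry is uniform from 6w0d (day 42). The 14 possible quit days are equally likely. One month is 30 days unless stated. The plan gives no figure of its own on this point to reproduce.

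**1. Order of visits (no lag needed).** Early follows late when entry day + 30 > 196, that is, entry after day 166 = 23w5d. With a 28-day month it is entry after day 168 = 24w0d.

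**2. Early visit against the quit date.** Days from quit date to early visit = 30 − L − q. The visit falls before day 7 (in or before the quit week) when 30 − L − q < 7, so q > 23 − L.

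| L | Days after quit date | Share before day 7 |
|---|---|---|
| 7 | 9 to 22 | 0/14 = 0% |
| 14 | 2 to 15 | 5/14 = 36% |
| 21 | −5 to 8 | 12/14 = 86% |

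The smallest L that affects anyone is 10 days (with q = 14), or 8 days if a month is 28 days. Gestational age does not enter.

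**3. Late visit at exactly 28w0d.** Quit day Q = entry day + L + q. The visit falls before day 7 when 196 − Q < 7, and before the quit date when 196 − Q < 0. Example for L = 7 and limit 25w0d: entry days 169 to 175 contribute 1 + 2 + … + 7 = 28 of 134 × 14 = 1,876 combinations, or 1.5%. Each range runs from entry limit 25w0d to 25w6d.

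| L | Before day 7 | Women of 60 | Before quit date |
|---|---|---|---|
| 7 | 1.5–4.6% | 0.9–2.8 | 0–1.1% |
| 14 | 5.6–9.6% | 3.4–5.8 | 1.5–4.6% |
| 21 | 10.8–14.6% | 6.5–8.8 | 5.6–9.6% |

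Moving the visit to 30w0d cuts the before-day-7 share to 0%, 0–1.1% and 1.5–4.6%. At 32w0d it is 0% for all three lags.

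**4. Illustrative power.** Exact enumeration of the uncorrected C-M-H test, 30 per arm, two-sided 0.05, at the earlier pilot's rates (37% vs 11%), gives 67.6%. Multiplying both rates by 1 − f, where f is the before-day-7 share, is the worst case in which nobody seen before day 7 can test negative. It gives 66.7–64.7%, 64.1–61.5% and 60.8–58.4% for the three lags. Taking f as the before-quit-date share gives 67.6–66.9%, 66.7–64.7% and 64.1–61.5%.

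**5. Proposed rule.** Let C be the gestational day of the call. Early = C + 28; late = max(196, C + 42).
- Latest quit date is C + 14, so early is at least 28 − 14 = 14 days after it, and late at least 42 − 14 = 28 days after it.
- Late minus early is at least 42 − 28 = 14 days.
- Late falls after 28w0d when entry day > 154 − L. The shares are 20.9–24.3%, 26.1–29.3% and 31.3–34.3% for the three lags.
- Latest visit: 175 + 7 + 42 = 224 = 32w0d, up to 181 + 21 + 42 = 244 = 34w6d.

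**The case against.** The strongest reply is that the opening summary and Inclusion/Exclusion Criteria put the late visit at 28 weeks or later, so staff can wait, and at 32 weeks the late-visit problem is gone. That limits the late-visit point, but the wording permits waiting without requiring it, and the section that schedules the visits says 28 weeks. The reversal of order likewise needs a late visit at or near 28w0d.

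The lag, the entry distribution and the actual visit week are all unknown. At a 7-day lag the early visit is safe and only about 1 to 3 late visits are touched. If the summary's quit-date rule applied, only late visits for entry at 25w1d to 25w6d would be affected. This stands, and is why the sizes are ranges.

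Abstinence at a fixed gestational age is also a legitimate target, and the schedule was chosen for comparison with the group's earlier trials. That supports keeping 28 weeks as the floor. It does not support a visit before the quit date.

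A reader might infer that the late-pregnancy comparison is biased towards one arm, or that power falls to 58%. The documents support neither. Both clocks start before assignment and run alike in both arms. The 58% needs the longest assumed lag, every visit at exactly 28w0d, and nobody negative before day 7, although the plan does not say which marker defines abstinence at these visits. Any dilution already in the pilot rates would make the loss smaller. That lag also leaves some 28w0d visits on or before the call, and Orientation Session says in one place that women "complete the treatment assignment phone call, after which study staff will provide them with the" CO monitor (another sentence there has it mailed beforehand), so some would slip later.

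A reader might also infer that the visits should be timed from the quit date. Each woman chooses that date after learning her arm, so visit timing could then differ by arm.

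**Conclusion.** The concern holds as a scheduling weakness worth correcting at little cost. Three parts rest on the text alone: the visits are not tied to the start of treatment, there is no minimum interval, and a literal reading puts early after late for entry beyond 23w5d (24w0d with a 28-day month).

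The rest depends on the unstated lag. Early visits in or before the quit week begin at a lag of about 8 to 10 days, reach about 36% at 14 days, and are not confined to late entrants. Late visits are affected less: 1.5 to 15% of women for lags of 7 to 21 days, uniform entry and a visit at exactly 28w0d, mainly those entering near 24 to 25 weeks, and none at 32 weeks.

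The consequence is modest dilution in both arms. Continuous abstinence and the postpartum comparisons are largely untouched. The summary's different starting point for the quit date is a separate, small inconsistency to correct at the same time.

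**What to change.** In Assessment Procedures, time both visits from the orientation/randomisation call, which does not depend on arm:

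- **Early:** 4 weeks after the call.
- **Late:** the later of 28w0d and 6 weeks after the call, with an upper limit before term (36w6d would not bind for lags up to 21 days) and one rule, the same in both arms, for women who deliver first.

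Use the wording of 28 weeks or later consistently in the opening summary, Assessment Procedures and Inclusion/Exclusion Criteria. In the summary, count the quit date from the orientation call. Report days from quit date to each visit by arm, so that readers can judge any remaining dilution.

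**Cost.** No visits are added and the late visit stays within 28 weeks or later. Under the assumptions above, about 21 to 34% of women would have it after 28w0d, the latest at 32w0d to 34w6d, so a few may deliver first. Research staff deliver the 5As at the pregnancy assessments, so that counselling moves with the visits in both arms. Comparability with the group's earlier trials is slightly reduced.
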